### **3.1.3        Communication Strategy**

After each HV receives RO7062931 (or placebo), the Investigator(s) must confirm to the Sponsor that the HV has been dosed and provide a brief summary of the status of the subject in terms of safety and tolerability to RO7062931/placebo (this will be communicated by email and/or telephone). The Investigator(s) will provide a safety assessment feedback of the first two sentinel dosing HVs of each cohort prior to dosing the remaining HVs enrolled in the cohort.

In case of a safety concern, the Investigator will contact the Sponsor immediately to discuss study subject status and action taken/to be taken. In addition, after each cohort has been completed, the Sponsor will organize a teleconference with the Investigator to discuss the safety and tolerability of RO7062931 and to discuss eventual next cohort(s) or continuation. During these teleconferences, adverse events (with severity assessed as given in [Table 1](#)) in addition to available safety laboratory results, vital signs, ECGs, will be discussed along with the results of the available PK data, and any other available data that may assist the dose-escalation decision process. The decision of these meetings will be documented in writing.

In addition to these communications, the Sponsor and Investigator(s) will be in regular contact throughout the study by email/telephone as per normal interactions during the conduct of a clinical study and the Sponsor will arrange regular teleconferences and meetings to discuss study status.

### **3.1.4        End of Study**

The end of the study is defined as the date the last subject's (HV's) last observation (LSLO) occurs. LSLO is expected to occur at the safety follow-up visit of the last HV enrolled.

## **3.2            RATIONALE FOR STUDY DESIGN**

Safety and PK of single RO7062931 doses will be characterized in HVs to determine the best liver-targeted dose to be evaluated in future studies in Chinese patients with CHB.

### **3.2.1        Rationale for Dosage Selection**

The anticipated dose levels for this study are 0.3 mg/kg, 1.0 mg/kg, 2.0 mg/kg and 3.0 mg/kg for Cohorts 1-4. In addition, based on the PK and safety evaluation of the top dose cohort and the available data from FIH Study BP39405, an optional fifth cohort (4.0 mg/kg) may be enrolled. All dose levels in this study will be within the dose range which has been demonstrated to be safe and well tolerated in the BP39405 study.

Doses up to 4.0 mg/kg are anticipated to be safe in humans

Data from the ongoing BP39405 study have shown that single doses of RO7062931 from 0.1 to 4.0 mg/kg were considered safe and well tolerated in healthy humans (Section 1.2.2). The planned starting dose of 0.3 mg/kg is higher than was used for the first EIH study, BP39405. The 0.3 mg/kg dose is chosen to minimize additional testing in Chinese HVs of doses that may not provide information. This starting dose would have a safety margin > 10-fold to the most sensitive species evaluated in GLP toxicology studies.

### **3.2.2 Rationale for Study Population**

Chinese healthy male and post-menopausal or surgically sterile female HVs of 18 to 60 years of age, inclusive, have been selected for this study, for the following reasons:

- A dedicated study in HVs is expected to provide a more consistent and robust assessment of safety, PK parameters and pharmacological effect in the absence of potentially confounding disease and medications.
- Unexpected adverse events or toxicities are usually better identified and easier to treat in HVs without co-morbid diseases or concomitant medications. At the dose and regimen selected, HVs have lower risk of developing clinically significant sequelae from potential temporary adverse events.
- The rate of incidental or sporadic findings that may interfere with the assessment of basic safety parameters or with meeting study objectives is likely to be lower in healthy individuals than in patients.

- The doses to be explored in this study, will have already been declared as safe and well tolerated in the BP39405 study.

### **3.2.3 Rationale for Control Group**

This Phase I study is designed to be adequate and well-controlled. Randomization to RO7062931 or placebo will occur in a 4:1 ratio within each of the up to 4 cohorts planned. This is considered sufficient to allow for comparisons of safety and tolerability of active drug to placebo both within and across cohorts.

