## **6. STATISTICAL CONSIDERATIONS AND ANALYSIS PLAN**

### **6.1 DETERMINATION OF SAMPLE SIZE**

The planned sample size of 8 active per cohort was chosen not only to allow adequate assessment of safety and tolerability but also to increase the precision of the estimates

of mean PK and urinary parameters, as comparisons of these parameters across doses will be used in part [REDACTED].

Up to 50 HVs will be included in this study. Up to 5 cohorts of 10 HVs (8 on active and 2 on placebo per dose level) are planned with the *fifth* and last cohort being optional and based on the analysis of emerging PK and safety data from this study and available data from study BP39405.

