## **6.5 SAFETY ANALYSES**

All safety analyses will be based on the safety analysis population.

The safety data, including adverse events, injection site reactions (ISRs), reason for withdrawal from study, laboratory data, ECG, concomitant medications, vital signs and physical examination results will be listed and summarized descriptively by treatment and dose level. All placebo patients will be pooled as one treatment group. Marked abnormalities will be flagged for laboratory data.

As appropriate, listings, summary tables and graphs (study subject plot and/or mean plots) will be provided for safety and tolerability assessments.

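### Does Section 3.2.3 promise active–placebo comparisons within cohorts that two placebo subjects per cohort cannot deliver?

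*Combined protocol and SAP*

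**What the plan says.** Section 3.2.3 (Rationale for Control Group) describes randomisation in a "4:1 ratio within each of the up to 4 cohorts planned" and then states: "This is considered sufficient to allow for comparisons of safety and tolerability of active drug to placebo both within and across cohorts".

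Other sections of the current text give the design and the analysis:

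- Section 6.1: "Up to 5 cohorts of 10 HVs (8 on active and 2 on placebo per dose level) are planned", and "Up to 50 HVs will be included in this study". Section 3.2.1 adds that "an optional fifth cohort (4.0 mg/kg) may be enrolled".
- Section 4.3 builds each cohort from a first pair (one active, one placebo) and a further eight (seven active, one placebo).
- Section 6.5: "All placebo patients will be pooled as one treatment group". Safety data are listed and summarised descriptively by treatment and dose level. Sections 6.2 and 6.4 pool placebo in the same way.
- Section 2.1 makes safety and tolerability against placebo the primary objective.

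No section gives a test, significance level, power or assumed event rate for active against placebo.

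**The concern.** The primary objective is comparative, and Section 3.2.3 is where the protocol says what its control group can support. It appears wrong in two ways. It counts four cohorts where the design has up to five, so a reader would infer 8 placebo subjects in total instead of up to 10. It also says that comparison within a cohort is adequate, although each cohort has two placebo subjects and Section 6 describes no such comparison.

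Doses are escalated cohort by cohort. If the sentence were taken at face value, a contrast of 8 against 2 might be given weight at an escalation meeting, or reported as a dose-level finding, when it carries almost no information.

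**Working it through.** **Inputs.** 8 active and 2 placebo per cohort (Sections 4.3 and 6.1); up to 5 cohorts and 50 subjects (Section 6.1); 4 cohorts (Section 3.2.3). The documents give no significance level or event rates. The two-sided 5% level and the rates below are assumptions, used only for illustration.

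**1. Cohort count.** 5 × (8 + 2) = 50, which reproduces the stated maximum. 4 × (8 + 2) = 40, which does not. Pooled placebo is 5 × 2 = 10 with the optional cohort and 4 × 2 = 8 without it. The amendment rationale lists the sections revised when cohorts were added as 3.1.1, 3.2.1, 6.1 and Figure 1. Section 3.2.3 is not listed, so its four looks like a missed update.

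**2. What 8 against 2 can show.** With no placebo events and *a* of 8 active subjects affected, the Fisher probability that both placebo subjects fall among the 10 − *a* unaffected is C(10 − *a*, 2) / C(10, 2):

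- *a* = 8: 1/45 = 0.022
- *a* = 7: 3/45 = 0.067
- *a* = 6: 6/45 = 0.133

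For these three tables the two-sided p-value is the same. With one placebo event, even 8/8 gives 2/10 = 0.20. An excess on active therefore reaches 5% only at 8/8 against 0/2.

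The upper two-sided 95% limit after 0 events in *n* subjects is 1 − 0.025^(1/*n*): 84% for *n* = 2, 37% for *n* = 8 and 31% for *n* = 10.

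Chance of p ≤ 0.05 under assumed true rates:

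| Active v placebo rate | 8 v 2 | 8 v 8 | 8 v 10 |
|---|---|---|---|
| 80% v 0% | 17% | 94% | 99% |
| 70% v 10% | 5% | 60% | 71% |
| 50% v 10% | 0.3% | 22% | 37% |

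The first two entries for 8 v 2 can be checked by hand: 0.8^8 = 0.168, and 0.7^8 × 0.9^2 = 0.047.

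For a continuous measure, the 95% half-width for a mean difference is t × √(1/n₁ + 1/n₀) in SD units: 1.82 SD for 8 v 2 and 1.01 SD for 8 v 10.

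**3. Does anything planned use 8 against 2?**

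- Safety summaries (Section 6.5): each dose level beside pooled placebo.
- Conduct and baseline summaries (Sections 6.2 and 6.4): pooled placebo.
- Numerical stopping criteria (Section 3.1.2.2): counts of drug-related findings among subjects on active drug, within one dose level or across two consecutive cohorts, with no placebo term.
- Escalation review (Section 3.1.2): safety data from at least 8 subjects, active or placebo, with no comparison between arms specified.
- Sample size (Section 6.1): argued from 8 active per cohort, with no claim of power against placebo.

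None of them does.

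**The case for a change.** The strongest case for a change is that the sentence fails even without a test. A reference rate that could be as high as 84% after zero events is no reference, so calling the contrast sufficient overstates it on descriptive grounds alone. Nor does pooling help at the first escalation: pooled placebo after *k* cohorts is 2*k*, so after Cohort 1 it is the same two subjects. A team that trusted Section 3.2.3 might then read too much into them. The cohort count is also a plain contradiction within current text, not a leftover in the amendment log.

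The arithmetic and the contradiction stand. The consequence does not follow. The section speaks of comparisons, not tests, and two concurrent placebo subjects do allow side-by-side review of profiles under the same cohort conditions. The plan attaches no inference to that review. Having only two placebo subjects at the first escalation follows from the 8:2 allocation, and deleting one word from a rationale would not alter it. That allocation is a fair trade-off in a descriptive Phase I study sized on its active subjects. The suggestion that escalation meetings would be misled is conjecture, because no written rule sends them to a contrast of 8 against 2.

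**Conclusion.** No change follows. The four in Section 3.2.3 is a clerical slip: Sections 3.1.1, 3.2.1 and 6.1 all give up to five cohorts, and only five reproduces the stated maximum of 50. Because the fifth cohort is optional, a pooled placebo group of 8 is also a legitimate outcome of the current design. The reference to comparison within cohorts is loose wording that matches no planned analysis. An analyst following Section 6 would compare each dose descriptively with 8 or 10 pooled placebo subjects, which is all that a corrected rationale would say.

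A same-cohort contrast is very imprecise (upper limit 84% after 0/2; half-width 1.82 SD), but it is not impossible and the plan does not rely on it. The Fisher and power figures rest on an assumed two-sided 5% level and assumed event rates, so they illustrate that imprecision and do not show a design failure. The conclusion that nothing changes does not depend on them. It rests on the pooling and descriptive summaries in Section 6 and on stopping criteria that count active subjects only.

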### **3.2.4 Rationale for Biomarker Assessments**

Complementary liver biomarkers, attempting to further characterize potential hepatic effects may include microRNA-122 (miRNA-122) and glutamate dehydrogenase (GLDH). According to [Hornby et al 2014](#), miRNA-122, a liver-enriched miRNA, has demonstrated its use both in animal and human studies as a sensitive and specific biomarker of drug induced liver injury (DILI) and may be elevated earlier than ALT. In addition, it has also been used as a marker of viral hepatitis; [Zhang et al 2010](#) reported that plasma miRNA-122 levels change in patients infected with HBV showing a disease-severity relationship and a strong correlation with plasma ALT activity.

In the pre-clinical studies (monkey and rat GLP studies) with RO7062931, increased levels of  $\alpha$ 1-microglobulin, kidney injury molecule (KIM)-1, neutrophil gelatinase-associated lipocalin (NGAL) and  $\beta$ 2-microglobulin were observed. In a first-in-human study, the treatment with the LNA antisense oligonucleotide SPC5001 ([Poelgeest et al 2015](#)) was associated with acute renal tubular toxicity at the highest dose tested. Therefore, urine kidney biomarkers  $\alpha$ 1-microglobulin,  $\beta$ 2-microglobulin and KIM-1 will be included in this study to evaluate potential acute kidney effects.

Based on non-clinical data (and class effect [Kynamro Solution for injection 189 mg, [CHMP-EMA Assessment Report 2013](#)]) RO7062931 is considered to be of low risk for acute reactions; however, cytokines and complement activation will be measured and sentinel dosing will be implemented.

## **3.3 OUTCOME MEASURES**

### **3.3.1 Safety Outcome Measures**

The safety outcome measures for this study are as follows:

- Incidence and severity of adverse events, including adverse events of special interest (see Section [5.1.3](#)).
- Incidence of laboratory abnormalities based on hematology, blood chemistry, coagulation and urinalysis test results (see Section [4.6.1.5](#)).
- ECGs (see Section [4.6.1.4](#)).
- Vital signs, including blood pressure, pulse rate and temperature (see Section [4.6.1.3](#)).

### **3.3.2 Pharmacokinetic Outcome Measures**

The PK evaluations for this study are as follows:

Blood and urine samples will be collected to evaluate the RO7062931 and if applicable metabolite(s) PK, as specified in the Schedule of Assessment tables (see [Appendix 1](#) and [Appendix 2](#)). Plasma and urine concentrations will be measured by specific validated methods.

The following plasma and urine PK parameters will be calculated for RO7062931 (and its metabolites, as appropriate), when possible, using non-compartmental methods:

- $C_{max}$ : maximum plasma concentration.
- $t_{max}$ : time to reach the maximum plasma concentration.
- $AUC_{0-inf}$ : area under the plasma concentration-time curve from time zero to infinity.
- $AUC_{0-last}$ : area under the plasma concentration-time curve from time zero until the last quantifiable time-point.
- Additional PK parameters may be calculated from available data including:  
 $k$  (terminal elimination rate constant),  
 $t_{1/2}$  (terminal elimination half-life),  
 $CL/F$  (apparent clearance) and  
 $V_z/F$  (apparent volume of distribution).
- Urine PK parameters may be calculated with available data including:
- $A_e$ : cumulative amount of drug excreted in urine over a 24 hour period or over defined time periods linked to the pools of urine collected.

### **3.3.3 Other outcome measures**

- Kidney biomarkers including urine  $\alpha 1$ -microglobulin,  $\beta 2$ -microglobulin and KIM-1.
- Liver biomarkers including, miRNA122 and GLDH.
- Assessments for inflammatory markers (complement, C-Reactive Protein [CRP], erythrocyte sedimentation rate [ESR], gamma globulin and the following inflammatory biomarkers [interleukin (IL)-6, IL-8, IL12, mast cell protease (MCP1), tumor necrosis factor (TNF) $\alpha$ ]), drug induced autoantibodies and anti-drug antibodies (ADA).

## **4. MATERIALS AND METHODS**

### **4.1 CENTER**

An additional site(s) may be included for back-up purposes and may be activated if needed. Administrative and Contact Information, and List of Investigators are provided separately.

## **4.2 STUDY POPULATION**

Healthy volunteers must satisfy all inclusion and exclusion criteria to be enrolled into the study. Under no circumstances are subjects who enroll in this study permitted to be re-randomized to another cohort of this study.

Study subjects who drop out of the study for non-safety reasons may be replaced to ensure sufficient data to characterize the safety, tolerability, and PK and/or to make dose-escalation decisions. Study subjects who withdraw from the study due to poor tolerability or for study drug-related adverse events will not be replaced.

### **4.2.1 Recruitment Procedures**

HVs will be identified for potential recruitment using pre-screening enrollment logs, Independent Ethics Committee (IEC)/ Institutional Review Board (IRB) approved newspaper/radio advertisements and mailing lists prior to consenting to take place on this study.

### **4.2.2 Inclusion Criteria**

HVs must meet the following criteria for study entry:

1. Chinese healthy male and female (of non-childbearing potential) volunteers. Healthy status is defined by absence of evidence of any active or chronic disease following a detailed medical and surgical history, concomitant drug use (including hormonal supplements), a complete physical examination including vital signs, 12-lead ECG, hematology, blood chemistry, serology and urinalysis.
2. 18 to 60 years of age, inclusive.
3. A Body Mass Index (BMI) between 19 to 27 kg/m^2 inclusive and a body weight of at least 45 kg.
4. Women should be of non-childbearing potential. *These include those who have undergone surgical sterilization (removal of ovaries and/or uterus) or are post-menopausal ( $\geq 12$  continuous months of amenorrhea with no identified cause other than menopause, confirmed by follicle-stimulating hormone [FSH]  $\geq LLN$  (Local Lab), or amenorrhea for at least 24 months if on hormone replacement therapy [HRT]).*

All males must agree to remain abstinent (refrain from heterosexual intercourse) or use contraceptive measures, and agree to refrain from donating sperm, as defined below:

With female partners of childbearing potential or pregnant female partners, men must remain abstinent or use a condom up to 105 days after the last RO7062931 dose to avoid exposing the embryo to the study drug. Men must refrain from donating sperm during this same period.

The reliability of sexual abstinence should be evaluated in relation to the duration of the clinical trial and the preferred and usual lifestyle of the HV. Periodic abstinence (e.g., calendar, ovulation, symptothermal, or post-ovulation methods) and withdrawal are not acceptable methods of contraception.

5. Able to participate and willing to give written informed consent and to comply with the study restrictions.
6. Non-smoker (nor tobacco containing products) for at least 90 days prior to dosing on Day 1 and agree to remain as non-smoker during the study.

#### **4.2.3 Exclusion Criteria**

HVs who meet any of the following criteria will be excluded from study entry:

1. Women who are lactating.
2. Any suspicion or history of alcohol and/or other substance abuse or dependence in the past 6 months.
3. Positive urine drug and alcohol screen (barbiturates, benzodiazepines, methadone, amphetamines, methamphetamines, opiates, cocaine, cannabinoids and alcohol), or positive cotinine test at *Screening or Day -1*.
4. Positive result on hepatitis B (HBV), hepatitis C (HCV), or human immunodeficiency virus (HIV)-1 and -2 at *Screening*.
5. Confirmed (e.g., two consecutive triplicate measurements) average systolic blood pressure (SBP)>140 or <90 mmHg, and diastolic blood pressure (DBP)>90 or <45 mmHg at *Screening or Day -1*.
6. Confirmed (e.g., two consecutive triplicate measurements) average resting pulse rate > 90 or < 45 beats per minute (bpm) at *Screening or Day -1*.
7. A personal history of unexplained blackouts or faints, or known risk factors for Torsade de Pointes (e.g., hypokalemia, heart failure). Clinically significant abnormal ECG, including arrhythmias or marked QT abnormalities (QTcF < 300 msec or >450 msec at *Screening or Day -1*).
8. ECG morphology at *Screening or Day -1* that renders measurement of QT interval imprecise (e.g., neuromuscular artifact that cannot be readily eliminated, indistinct QRS onset, low amplitude T-wave, merged T- and U-waves, prominent U-waves, arrhythmias, etc.).
9. Screening or baseline ECG evidence of atrial fibrillation, atrial flutter, complete right or left bundle branch block, Wolff-Parkinson-White syndrome, or cardiac pacemaker.
10. Personal or family history of congenital long QT syndrome or sudden death.
11. *Any out of range findings in liver function tests, INR and renal function tests or any clinically significant abnormalities (as judged by the Investigator) in the physical examination and in the remaining laboratory test results (including hepatic and renal panels, complete blood count, chemistry panel and urinalysis) at Screening or on Day-1. Abnormal renal function including serum creatinine > ULN (Local Lab) or calculated creatinine clearance < 70 mL/min (using the Cockcroft Gault formula).*

12. Participation in an investigational drug or device study within 90 days prior to Screening or 5 times the half-life of the investigational drug (whichever is longer).
13. Donation of blood over 500 mL within three months prior to Screening.
14. Concomitant disease or condition (including allergic reactions against any drug, or multiple allergies) that could interfere with, or treatment of which might interfere with, the conduct of the study, or that would, in the opinion of the Investigator, pose an unacceptable risk to the healthy subject in this study.
15. Any major illness within the one month preceding the Screening visit, or any febrile illness within the two weeks preceding the Screening visit.
16. Alcohol consumption of more than 2 standard drinks per day on average; 1 standard drink equals 10 grams of alcohol (for further guidance please see [Appendix 3](#)) and/or drug abuse within one year of randomization.
17. Hypersensitivity to the excipients of the study drug.
18. HVs under judicial supervision, guardianship or curatorship.

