### **Exclusion criteria:**

Healthy volunteers who meet any of the below criteria will be excluded from study entry.

1. Women who are lactating.
2. Any suspicion or history of alcohol and/or other substance abuse or dependence in the past 6 months.
3. Positive urine drug and alcohol screen (barbiturates, benzodiazepines, methadone, amphetamines, methamphetamines, opiates, cocaine, cannabinoids and alcohol), or

---

---

positive cotinine test at *Screening or Day -1*.

4. Positive result on hepatitis B (HBV), hepatitis C (HCV), or human immunodeficiency virus (HIV)-1 and -2 *at Screening*.
5. Confirmed (e.g., two consecutive triplicate measurements) average systolic blood pressure (SBP) > 140 or < 90 mmHg, and diastolic blood pressure (DBP) > 90 or < 45 mmHg *at Screening or Day -1*.
6. Confirmed (e.g., two consecutive triplicate measurements) average resting pulse rate > 90 or < 45 beats per minute (bpm) *at Screening or Day -1*.
7. A personal history of unexplained blackouts or faints, or known risk factors for Torsade de Pointes (e.g., hypokalemia, heart failure). Clinically significant abnormal ECG, including arrhythmias or marked QT abnormalities (QTcF < 300 msec or > 450 msec *at Screening or Day -1*).
8. ECG morphology *at Screening or Day -1* that renders measurement of QT interval imprecise (e.g., neuromuscular artifact that cannot be readily eliminated, indistinct QRS onset, low amplitude T-wave, merged T- and U-waves, prominent U-waves, arrhythmias, etc.).
9. Screening or baseline ECG evidence of atrial fibrillation, atrial flutter, complete right or left bundle branch block, Wolff-Parkinson-White syndrome, or cardiac pacemaker.
10. Personal or family history of congenital long QT syndrome or sudden death.
11. *Any out of range findings in liver function tests, INR and renal function tests or any clinically significant abnormalities (as judged by the Investigator) in the physical examination and in the remaining laboratory test results (including hepatic and renal panels, complete blood count, chemistry panel and urinalysis) at Screening or on Day -1. Abnormal renal function including serum creatinine > ULN (Local Lab) or calculated creatinine clearance <70 mL/min (using the Cockcroft Gault formula).*
12. Participation in an investigational drug or device study within 90 days prior to Screening or 5 times the half-life of the investigational drug (whichever is longer).
13. Donation of blood over 500 mL within three months prior to Screening.

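### Exclusion criterion 5 joins the systolic and diastolic limits with *and*, so read literally it does not exclude a volunteer with only one of them confirmed out of range

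*Combined protocol and SAP*

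**What the plan says.** Section 4.2.3, criterion 5, excludes volunteers whose confirmed readings at Screening or Day -1 show "average systolic blood pressure (SBP)>140 or <90 mmHg, and diastolic blood pressure (DBP)>90 or <45 mmHg". Two consecutive triplicate measurements are given as an example of confirmation. The synopsis carries the same rule with the same connective: "average systolic blood pressure (SBP) > 140 or < 90 mmHg, and diastolic blood pressure (DBP) > 90 or < 45 mmHg".

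The lead-in to the list says that meeting any one criterion excludes. That governs how the numbered criteria relate to each other. It does not settle the *and* inside criterion 5.

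Three other places bear on how to read it:

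- Criterion 6 sets a two-sided limit on pulse alone, in the same format: "average resting pulse rate > 90 or < 45 beats per minute (bpm".
- Criterion 4 refers to a positive result for "human immunodeficiency virus (HIV)-1 and -2", and criterion 11 begins "Any out of range findings in liver function tests, INR and renal function tests". In both, *and* links items that each count alone.
- Blood pressure is also covered without numbers. Inclusion criterion 1 (section 4.2.2) says "Healthy status is defined by absence of evidence of any active or chronic disease", judged after, among other things, "a complete physical examination including vital signs". Exclusion criterion 11 adds "any clinically significant abnormalities (as judged by the Investigator) in the physical examination". Exclusion criterion 14 covers any condition that the investigator considers an unacceptable risk.

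**The concern.** In criterion 5 the contrast between *or* within each range and *and* between the ranges naturally signals a joint condition. A site that follows the words would find that a volunteer with a confirmed systolic or diastolic value outside its range, and the other inside, does not meet the criterion.

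This is an operative entry threshold. It is applied to every volunteer at Screening and again at Day -1, and the investigator's assessment against the criteria is documented on the Eligibility Screening Form (section 4.6.2.1). Blood pressure is a named safety outcome (section 3.3.1). A numeric limit exists so that borderline volunteers are handled alike without relying on judgement, and section 4.1 allows back-up sites to be activated. Two readers could apply this limit differently to the same volunteer.

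**Working it through.** No sample size, power or error rate rests on this criterion, so the check is one of logic. The limits come from criterion 5 itself.

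Let S mean that SBP is >140 or <90 mmHg, and D that DBP is >90 or <45 mmHg.

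- Joint reading (literal *and*): criterion met if S and D.
- Separate reading: criterion met if S or D.

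The two readings differ exactly when one of S and D is true and the other false, that is, for isolated abnormalities. The pressures below are illustrative confirmed averages, not trial data.

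| Confirmed average (mmHg) | S | D | Joint reading | Separate reading |
|---|---|---|---|---|
| 144/80 | yes (high) | no | not met | met |
| 132/94 | no | yes (high) | not met | met |
| 86/56 | yes (low) | no | not met | met |
| 104/43 | no | yes (low) | not met | met |
| 144/94 | yes (high) | yes (high) | met | met |
| 140/90 | no | no | not met | not met |

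Counting categories gives the same result. Three systolic bands times three diastolic bands make 9 combinations. One has both in range, leaving 9 − 1 = 8 with something out of range.

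- Isolated: 2 (systolic out, diastolic in) + 2 (diastolic out, systolic in) = 4.
- Both out: 2 × 2 = 4. One of these (SBP <90 with DBP >90) cannot occur, which leaves 3.

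The joint reading therefore covers 4 of 8 combinations (3 of the 7 attainable) and none of the 4 isolated ones. The separate reading covers 8 of 8 (7 of 7). These are cells of a logic table and carry no information on how often each occurs.

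Next, does anything else in the plan close the gap?

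- Another numeric limit: none of the other inclusion or exclusion criteria gives one for blood pressure.
- A statement that one value suffices: none was found.
- Judgement-based cover: inclusion 1 and exclusions 11 and 14, as described above. Clear hypertension should be caught under inclusion 1 as evidence of disease. A marginal value, or an isolated low one, is where investigators could reasonably differ.

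**The case against.** The strongest reply is that any experienced site will read two separate limits. The list often uses *and* for items that each count alone: in criteria 4 and 11, and also in criterion 3, where drug and alcohol testing are paired. Criterion 6 is a stand-alone limit. On that usage criterion 5 can already be read as the intended rule. This stands as evidence of intent. It does not fix the wording, because none of those examples joins two numeric ranges that each contain their own *or*.

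A second reply is that the consequence is small. That also stands. Appendix 2 schedules vital signs at Screening, Day -1 and pre-dose, so each volunteer has reference readings. The counted stopping rules in section 3.1.2.2 require clinically significant, drug-related changes, so an abnormal baseline alone does not trigger them.

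A reader might infer more than the documents support:

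- *That volunteers with hypertension will be enrolled.* The text can be read as requiring both values, but it need not be, and the judgement-based criteria remain. An ambiguity is shown; a missed exclusion is not.
- *That the pharmacokinetic population would change.* Section 6.3.2 removes only significant violations, with reasons documented and decisions made before database closure. Nothing suggests that an isolated marginal pressure would count as significant.
- *That the impossible pairing of low systolic with high diastolic shows an error.* That cell appears in any crossing of two two-sided limits, and the separate reading covers it too, so it does not favour either reading.
- *That strict operator order (and before or) is a third reading.* The printed comma groups each range, and nothing in the text supports ignoring it.

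**Conclusion.** The point holds as a wording defect in an operative entry criterion. On its literal reading, criterion 5 requires both pressures to be out of range and does not exclude any of the four kinds of confirmed isolated abnormality. Two separate limits were probably meant, but this is inferred from the style of the list and is not stated anywhere.

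Its size is modest. The practical gap is mainly marginal or isolated low values, because the judgement-based criteria should catch clear disease. How many volunteers this could affect is unknown: the documents give no blood pressure distribution. No analysis, sample size, error rate or stopping rule changes.

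The conclusion rests on two assumptions: that a site may apply the printed connective literally, and that no site instruction outside these documents already settles the reading. The numeric limits themselves are not questioned. The correction is still worth making, since it is a healthy-volunteer entry threshold and the repair is almost free.

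**What to change.** In section 4.2.3 and in the synopsis, keep all four limits as they are and replace *and* with *or* between the systolic and diastolic limits, so that either value, once confirmed out of range, meets the criterion. The sponsor should confirm that this is the intent. If a joint condition is intended instead, both places should say explicitly that systolic and diastolic must both be out of range.

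The cost is one connective in two places. There may be a few more screen failures where the literal wording was being applied, and none where the limits are already read separately.
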